Kinase pathways. In addition, treatment with standard oral medications such as triple oral disease modifying drugs (DMARDs) also are effective options (7). Despite these advances, a large percentage of our patients require daily therapy with oral prednisone and/or don't respond to these current therapies. Thus, safe new therapies are still needed for this common immune-mediated inflammatory disease.

B. Hypothesis and Specific Aims:

Hypothesis: Patients with RA, who are receiving stable doses of background medications will have an improvement in disease activity (as measured by CDAI) when treated with 12 weeks of subcutaneous ACTHAR.

Specific aim 1: To determine the efficacy and safety of ACTH gel in refractory RA patients.

Specific aim 2: To determine the potential mechanisms of action of ACTH gel, pending review of efficacy data.

C. STUDY Design:

The proposed trial design would be open-label with a subcutaneous dose of ACTHAR 80 units, twice a week, for 12 weeks. The entry criteria would be:

1. RA diagnosis by ACR criteria
2. Active disease (CDAI > 10) (8, 9, 10)
3. Have received at least one biologic agent for at least 6 months

4. May or may not be receiving oral daily steroids (less than or equal to 20 mg/day) of prednisone equivalent
5. No current active infections requiring antibiotics
6. Patients must be on stable doses of RA therapies (e.g., methotrexate or other RA therapies for at least 4 weeks prior to baseline visit)

Table 1. Proposed Study Visits and Study Activities

	Screening	Baseline	2wk	4wk	8wk	12wk	16wk
Informed Consent	X						
Dispense medication		X		X	X	X	
Clinical Labs*	X		X	X	X	X	X
AE Monitoring			X	X	X	X	X
Efficacy assessments		X	X	X	X	X	X
Research Labs (PBMC's, serum, plasma, RNA)		X	X	X	X	X	X

*CBC, glucose, creatinine, ESR, CRP, ALT

Patient population and estimated sample size: Patients will be recruited from UPMC Rheumatology Outpatient Clinics. A pilot study of 20 patients will provide initial information on efficacy of this agent in refractory RA patients. For the year ending in Spring 2012, we had over 4,000 unique, active RA patients in our outpatient clinics. We have 35 Rheumatologists who practice at UPMC in Western, PA.

Primary end-points:

1. Changes in CDAI at week-12 (9); we propose a 20% improvement after 12 week of therapy compared to baseline as a positive response.

Secondary end points:

1. Changes in DAS28-CRP (9, 10)
2. Changes in acute phase reactants (ESR, CRP)

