3. Changes in fatigue, as measured by FACIT (11).

D. Data Analysis:

We will determine the frequency of subjects who have at least a 20% improvement in CDAI from baseline to week 12 visit. We will document the frequency and events of adverse event. For secondary endpoints we will also determine frequency of subjects what have at least 20% improvement in DAS28-CRP, fatigue, ESR and CRP from baseline to week 12.

E. Data captured and Database:

The Division of Rheumatology and Clinical Immunology has experience spanning four decades in the development, maintenance and refinement of disease-specific databases of longitudinal cohorts of patients with rheumatic diseases. In the past few years we have developed a web-based database that we plan to use for this investigator-initiated trial. The key characteristics of the Rheumatic Disease Musculoskeletal System (RDMS) are: **1)** the ability for longitudinal data collection and database management of data

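### ESR and CRP are summarised only by a count of 20% improvers, which discards the size of the change and has a sizeable, unknown chance rate in 20 uncontrolled patients

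*Combined protocol and SAP*

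**What the plan says.** Section C (Secondary end points) lists "Changes in acute phase reactants (ESR, CRP") without a threshold or subset. Section D (Data Analysis) then reports, for the secondary endpoints, the frequency of patients with "at least 20% improvement in DAS28-CRP, fatigue, ESR and CRP from baseline to week 12". It gives no continuous summary, confidence interval, minimum baseline value, rule for results below a reporting limit, or denominator.

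Among the six entry criteria in Section C, the only disease-activity threshold is "Active disease (CDAI > 10"). None refers to ESR or CRP. Both markers are measured as routine laboratory tests (Table 1 footnote: "CBC, glucose, creatinine, ESR, CRP, ALT").

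The design is open label with one regimen, and no control group is described. On sample size, Section C says: "A pilot study of 20 patients will provide initial information on efficacy of this agent in refractory RA patients".

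**The concern.** A percentage cut turns a measured change into yes or no. A 19% fall and no fall count the same, and so do a 20% fall and an 80% fall. With 20 patients, that loses much of what the markers can say.

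The count is also hard to read. ESR and CRP move between two measurements even when the disease does not, so some patients pass a 20% cut by chance. A control group would show roughly how many. Here there is none, and the plan states no reference rate. A report of, say, 6 of 20 patients improved on CRP could reflect drug effect or ordinary variation, and the planned analysis could not tell a reader which is more plausible.

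The cut can also miss in the other direction. Entry sets no minimum ESR or CRP, so a patient may start at the laboratory's reporting limit. That patient cannot show a 20% fall, and Section D does not say how such a patient is handled.

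**Working it through.** There is no figure in the plan to reproduce: no variability, expected response rate or chance rate is given. The check asks how often a patient with no true change would meet the 20% rule.

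**Inputs from the documents:** a cut of at least 20% improvement from baseline to week 12 (Section D); 20 patients (Section C); no ESR or CRP requirement at entry (Section C).

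**Assumed inputs:** a within-person CV of 10% to 50%; log-normal variation; independent errors at the two visits.

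**Step 1: chance of a 20% fall with no true change.** With s = sqrt(ln(1 + CV²)), the log ratio of week 12 to baseline has mean 0 and SD sqrt(2) × s. The patient is counted if the log ratio is at or below ln 0.8 = −0.223, so P = Φ(ln 0.8 / (sqrt(2) × s)).

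| Assumed CV | sqrt(2) × s | P | Expected count of 20 |
|---|---|---|---|
| 10% | 0.141 | 0.057 | 1.1 |
| 20% | 0.280 | 0.213 | 4.3 |
| 30% | 0.415 | 0.295 | 5.9 |
| 40% | 0.545 | 0.341 | 6.8 |
| 50% | 0.668 | 0.369 | 7.4 |

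At a CV of 30%, the binomial probability of 5 or more such patients among 20 is 0.75. The formula contains no baseline level, so in this model P is the same for a low and a high starting value.

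**Step 2: the same data as a ratio.** With no true change the expected geometric mean ratio is 1. At a CV of 30% the standard error of the mean log ratio is 0.415 / sqrt(20) = 0.093. With the t quantile on 19 degrees of freedom (2.093), the half-width is 0.194. The 95% interval is then typically about exp(−0.194) = 0.82 to exp(0.194) = 1.21. The same noise that yields about 6 apparent improvers gives a ratio centred on 1 with a visible interval. This width allows for within-person noise only; patients who differ in true response would widen it.

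**Step 3: would restricting the count to patients with raised values help?** The Step 1 model was simulated with no true change and an assumed between-person log-SD of 0.8. A cut at the median observed baseline stood in for the upper limit of normal.

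| Assumed CV | P, all patients | P, above cut | P, below cut |
|---|---|---|---|
| 20% | 0.21 | 0.25 | 0.17 |
| 30% | 0.30 | 0.36 | 0.23 |
| 40% | 0.34 | 0.43 | 0.25 |
| 50% | 0.37 | 0.48 | 0.26 |

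The direction is the same at log-SDs of 0.6 and 1.0. Choosing patients because their baseline is high also selects upward error, which falls back at the next measurement. Restriction therefore raises the chance rate.

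**The case against.** **It is a small descriptive pilot.** No test is planned on ESR or CRP, the plan does not use them to support the primary, and the 20% convention matches that for CDAI, which is likewise listed as a change and analysed as a response. This stands, and it sets the weight of the point. It does not remove it: the pilot is meant to inform on efficacy, and the count is the only summary planned for these markers.

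**The size is assumed.** This also stands. The documents give no CV, reporting limit or share of patients with normal values. The span of 6% to 37% comes from the CVs chosen.

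**The tempting stronger reading.** Because entry requires no raised marker, a reader might infer that noise in near-normal values is what inflates the count, and that the remedy is to count only patients above the upper limit of normal. The documents do not support this. Under proportional noise the chance rate does not depend on baseline (Step 1), and the restriction makes it worse (Step 3). Near-normal values are more prone to false response if the noise is constant in absolute units. Then P = Φ(−0.2B / (SD × sqrt(1 + 0.8²))) for a true level B, and an assumed SD of 4 units gives 34.8% at 10, 21.7% at 20, 5.9% at 40 and 1.0% at 60. Nothing in the documents says that this model applies. A patient at the reporting limit lowers the count rather than raising it. Nor does Section D say that every patient stays in the denominator; it states none.

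**Scope.** The argument covers ESR and CRP. It is not a case for changing the analysis of DAS28-CRP or fatigue.

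**Conclusion.** The point holds in a limited form. Section D reduces change in ESR and CRP to a 20% count and plans no measure of its size. With no control group and 20 patients, the count has a chance rate that is unknown and may be sizeable: about 1 to 7 of 20 with no true change. That range rests on assumed within-person CVs of 10% to 50%, log-normal variation and independent errors. What does not rest on them is that magnitude is discarded, that the design offers no way to see the chance rate, and that a baseline at the reporting limit rules out a 20% fall.

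The CDAI primary endpoint is untouched. This is a minor improvement to a secondary analysis.

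**What to change.** In Section D, for ESR and CRP:

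- Make the geometric mean ratio of week 12 to baseline, with a 95% confidence interval, the main summary. Compute it from paired log values.
- State in advance one fixed value to substitute for any result below the laboratory's reporting limit, and report how many results were substituted.
- Say which measurement is the baseline. Table 1 marks the clinical laboratory tests at screening and from week 2, but not at the baseline visit.
- Keep the 20% frequency, if wanted, as a descriptive count in all patients with its denominator shown. Do not restrict it to patients above the upper limit of normal, because without a control group that adds regression to the mean.

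The cost is a few lines in Section D and a few table rows. The analysis uses ESR and CRP results already scheduled, and needs no extra patients.
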